## **DOCUMENT HISTORY**

Summary of change: not applicable.

| Document   | Date of Issue | Summary of Change |
|--|---------------|-------------------|
| Draft version                                    | 23-Dec-2021   | Not Applicable    |
| Consolidated version                             | 18-Feb-2022   | Not Applicable    |
| Final version (to be submitted Ethics Committee) | 30-Apr-2022   | Not applicable    |

#### **SYNOPSIS**

## **Observational Study Protocol PENTAGON**

#### **Protocol Title:**

PENTAGON: An observational, non-interventional, multicenter, prospective study to explore the association of MS-related disability worsening and loss of thalamus volume.

**Department:** Not applicable

#### **Objective:**

To demonstrate that the change of MS-related disability during a period of 24 months is inversely associated with change of thalamus volume during the same period.

Secondary Objectives

- (S1) To demonstrate that worsening of MS-related disability is associated with loss of thalamus volume when loss of whole brain volume is within the normal range.
- (S2) To demonstrate that the change of thalamus volume during 24 months is predictive of the change of disability during the following 12 months (months 24-36).

#### **Study Design:**

PENTAGON is a non-interventional, multicenter, prospective, observational study of active multiple sclerosis patients either already receiving or about to receive first-line oral therapy. Primary data will be collected for each study participant over a 24-month period. MS-related disability is characterized by the EDSS. The EDSS is determined at inclusion (baseline), 24 months after inclusion, and at additional visits at intervals of approx. every 6 months in between. Each study subject will undergo three brain MRI examinations using a standardized acquisition protocol following the 2021 MAGNIMS-CMSC-NAIMS consensus recommendations and including a high-resolution T1w MRI at affiliated radiology centers. The study will continue for an additional 12 months only if sample size requirements (minimum number of study patients at month 24) are met that indicate that the secondary outcome (S2) is sufficiently likely to be achieved. In a 6-month period preceding the primary data collection secondary data will be explored to confirm the validity of the statistical design and of the methodology.

#### **Study Population:**

The study population is defined by 600 study subjects with a diagnosis of relapsing-remitting MS aged 18 – 55 years, who either already receive or are about to receive first-line oral immune therapies with more than 10 T2 lesions or with active disease as defined by clinical (relapses) or imaging features (new/enlarging T2 lesions, Gd-enhancing lesions).

#### **Data Collection Methods:**

Three types of data will be collected: (1) clinical status, such as therapy change and relapse activity, (2) clinical scores, such as EDSS, and brain MRIs using a standardized protocol including a high-resolution T1w-MRI, at 20 study centers (neurology centers) and affiliated radiology centers in Germany. No procedures are mandatory, and no additional procedures are required beyond the standard examination of MS patients in routine clinical practice (standard-of-care). The EDSS will be assessed in a standardized manner. Evaluators at the study sites record clinical data and information required for the study after each patient visit and enter it into case report forms that are provided by the investigator. Affiliated radiology centers perform brain MRI scans according to standardized protocols, implemented together with the investigator, and transmit the image data to the investigator. Data privacy and security are ensured. Patient data are pseudonymized. The investigator can rely on an established infrastructure and a dense network of study centers and affiliated radiology centers. The processes and procedures are embedded in the clinical routine and have been successfully practiced since 2015.

Date: 23-Dec-2021 (revised 18-Feb 2022)

#### **Data Analyses:**

The year-to-year change in EDSS during the 24-month period is calculated by linear regression of EDSS against time, accounting for all visits. The slope of the regression line is the annual change in EDSS. For the correlation analysis, the annual change in EDSS and annualized TVL are considered continuous variables. Three high-resolution T1w MRI scans will be available for all study participants. TVL will be calculated for each pair of two consecutive MRI scans using an advanced and validated method from Opfer et al (2020) that is less susceptible to noise and therefore can estimate TVL in individual subjects. The annualized TVL between the baseline scan (BL) and the last follow-up scan (FU) is calculated by multiplying the TVL between the 2 consecutive scans and dividing the resulting TVL by the time interval between the BL and FU scans. A Pearson correlation analysis is used to test for a significance level of p = 0.05.

#### Sample Size/Power:

The primary objective is to demonstrate whether the correlation between the change in MS-related disability and the change in thalamic volume is significantly different from zero. Both the change in MS-related disability and the change in thalamic volume are continuous variables. Pearson's correlation analysis is performed assuming an expected correlation coefficient of 0.15. Assuming a type I error of 0.05 and a type II error of 0.20, the required sample size is 347, 24 months after the baseline EDSS measurement. Considering an annual dropout rate of 15% to 20%, the total sample size required is approximately 500 to 600 subjects to be enrolled in the study.

#### **Limitations/Strengths:**

The PENTAGON study is relatively long due to the inclusion of longitudinal parameters of brain atrophy to ensure that these parameters are reliably measured in individual subjects.

If the PENTAGON study is successfully completed, it will relate the results of the Phase III clinical trials (RADIANCE and SUNBEAM) regarding the effect of current and future disease modifying drugs on brain volume and, in particular, focal brain volume loss, to disability progression in a real-world setting. The number of disabling events required to meet the study endpoints is critical. The study population is enriched by careful definition of inclusion criteria. However, it remains a challenge to find the right balance between overly stringent inclusion criteria, the ability to enroll a sufficient number of study participants, and the risk of too many patients switching therapies during the course of the study. This balance requires continuous monitoring by the reviewers and the study team, which must determine timely actions. Once pathological TVL is confirmed, it could be considered a risk factor for disability worsening. This would then justify the inclusion of TVL in the spectrum of treatment targets in MS.

Date: 23-Dec-2021 (revised 18-Feb 2022)

#### 1. INTRODUCTION

[figure not shown]
## **Study Rationale**

The clinical course of multiple sclerosis (MS) is heterogeneous between patients and as of yet largely unpredictable on the single subject level. In addition to inflammatory demyelination and astrogliosis, neurodegeneration – a term that refers to structural axonal and neuronal damage plays a crucial role in the accrual of disability over time. An increasing body of evidence suggests that whole brain volume loss is indicative of disability progression (Sastre-Garriga et al. 2020). The mounting evidence prompted the MS community to add whole brain volume loss as a marker of tissue damage to the no-evidence-of-disease-activity (NEDA) concept. Since 2015 Germany-wide projects, such as QUANTUM, PANGAEA, MAGNON, have helped to establish a network of radiologists and neurologists for which accurate measurement and usage of whole brain volume loss (BVL) has become a "de-facto standard-of-care" (Schuh et al. 2020). Meanwhile, a solid connection between radiology centers, neurology centers and the investigator has developed. Through this network, thousands of MS patients in Germany recently received standardized MRI procedures for disease and therapy monitoring in routine clinical practice, providing hundreds of neurological centers in Germany with regular quantitative information on BVL and lesion activity.

The proposed study has the upside to build on this unique, large network and contribute to better understanding to what extent thalamus volume loss (TVL) appears as an independent driver of disability progression in early MS patients. Once proven and confirmed independently, TVL could serve as a potentially complementary marker of disease activity and a treatment target in future clinical practice, should surrogacy for disability progression be proven. Previous work has provided some important evidence rendering such ambitious goals within sight:

- 1. In the SUNBEAM and RADIANCE phase III trials, MS patients in the OZANIMOD groups showed a significant slowing of cortical gray matter and thalamic volume loss as compared to an active comparator (Cohen et al. 2019; Comi et al. 2019).
- 2. Opfer et al. (2020) demonstrated that TVL and BVL in MS patients do not necessarily go hand in hand (Fig. 1). This means, an MS patient with pathological TVL does not necessarily show a pathological BVL. It was hypothesized that TVL and BVL are "distinct" features of neurodegeneration, potentially driven by different underlying mechanisms that would warrant further research.
- 3. Results by Hänninen et al. (2019) suggest that thalamic atrophy rather than whole brain atrophy is a driver for disability worsening based on an assessment of 24 relapsing MS and 36 secondary-progressive MS patients.
- 4. Eshaghi et al. (2018) demonstrated that specifically deep gray matter volume loss is associated with disability progression, however, the technological pipeline which generated these results is susceptible to noise and thus is not yet applicable to decision making in single subjects under clinical routine conditions. This was addressed by Opfer et al. (2020) who presented and validated a technology which can identify pathological thalamic and deep gray matter volume

loss on a single subject level with a type II error of 5%. Furthermore, cut-offs were provided for application to individual patients in routine patient care.

**Figure 1.** Scatter plot of deep gray matter brain volume loss representing TVL as a function of BVL (Opfer et al. 2020).

However, despite the evidence generated so far and outlined above, the scarcity of data and the limited number of subjects in the respective studies do not yet allow a firm conclusion that pathological and non-pathological TVL of MS patients with normal BVL generate distinct subgroups or "endophenotypes" of MS. Once confirmed in a sample size powered for this analysis in a true longitudinal setting, pathological TVL could be considered a risk factor for disability worsening. This would then justify inclusion of TVL into the spectrum of treatment targets in MS.

#### **Research Question**

The research question is whether TVL is a driver of disability progression in MS patients. If this hypothesis were proven to be true this would qualify pathological TVL to be suitable as a treatment target for slowing disability progression.

#### 2. OBJECTIVES

## **Primary Objective**

To demonstrate that the change of MS-related disability during a period of 24 months is inversely associated with the change of thalamus volume during the same period.

## **Secondary Objectives**

- (S1) To demonstrate that worsening of MS-related disability is associated with loss of thalamus volume when loss of whole brain volume is within the normal range.
- (S2) To demonstrate the change of thalamus volume during 24 months is predictive of the change of disability during the following 12 months (months 24-36).

[figure not shown]
#### **Exploratory Objectives**

We will explore deep gray matter volume loss (DGMVL) in addition to TVL along the same objectives.

#### 3. STUDY DESIGN

## **Overview of Study Design**

#### Overall description

*Figure 2.* Study schedule and composition.

The PENTAGON study is an observational, non-interventional, multicenter, prospective, cohort study of active multiple sclerosis patients who either already receive or are about to receive first-line oral immune therapies with a preceding 6-month retrospective period for assessing the validity of the statistical design and of the methodology using secondary data.

### Start-up phase

A suitable MS cohort of secondary data, in particular those with MRI and EDSS scores, will be created using proprietary databases and databases collected from 2 to 3 collaboration partners in Germany and Switzerland. The data is heterogeneous in nature, comprising relapsing-remitting and secondary progressive MS patients, treated with multiple therapy regimens and of all ages. We will ensure that the MRIs included into the secondary data collection adhere to a minimum quality standard so that we are able to successfully apply and advance the technology developed in Opfer et al. (2020) and that there are sufficient EDSS data points for each individual patient available to test the validity of the inclusion criteria and the statistical design:

Among others, we are going to explore the following questions:

- Is sampling of the SDMT for a subgroup feasible in the context of this observational study and would this clinical score add value to help accomplish the secondary objective (S2)?
- Would the status of brain volume (whole brain, thalamus) as additional inclusion criterion help to enrich the patient population with disability events?
- How valuable is to consider total T2 lesion load as an inclusion criterion or should it be removed as a inclusion criterion in order to make the potential results of the study more applicable to the real world?

In parallel preparations will start for submission of the necessary documents for approval by ethics committees.

The following table provides checkmarks and / or milestones for the startup phase:

| ID  | checkmark / milestone description   | Type (mandatory / optional) | Due date (in
months after
official launch) |
|-----|---|-----------------------------|--|
| M-1 | Contract in place   | mandatory                   | 0  |
| M-2 | Secondary data set of minimum 150 MS patients assembled                                     | mandatory                   | +2   |
| M-3 | Ethics committee's approval in place  | mandatory                   | +3   |
| M-4 | Data exploration completed and conclusions regarding statistical design drawn               | mandatory                   | +5   |
| M-5 | Interim analysis completed (go / no-go-decision)  | mandatory                   | +5   |
| M-6 | Technology sufficiently advanced to warrant application on primary data; final report ready | mandatory                   | +6   |
| M-7 | Manuscript prepared for submission to a clinical optiona /technical journal                 |                             | +8   |

#### Main phase

Once ethics committee approval has been granted, enrollment of the first patients in the prospective observational study will begin. Enrollment of the first patients is planned 3 months after the official project launch. The enrollment period will last 9 months. Each study subject will be followed for 24 months. The EDSS is collected at inclusion (baseline), 24 months post baseline, and at additional visits at intervals of approx. every 6 months in between. Each study subject will undergo three brain MRI examinations using a standardized acquisition protocol following the 2021

MAGNIMS-CMSC-NAIMS consensus recommendations and including a high-resolution T1w MRI at affiliated radiology centers.

The following table provides checkmarks and / or milestones for the main phase including the extension period:

| ID   | checkmark / milestone description   | Type (mandatory / optional) | Due date (in
months after
official launch) |
|------|---|-----------------------------|--|
| M-8  | Launch of the prospective observational study at the investigator's own risk; first patient enrolled  | optional                    | +3   |
| M-9  | Last patient enrolled; baseline brain MRI examination (V1) for approx. more than 500 enrolled study subjects completed                                    | Mandatory                   | +12  |
| M-10 | V2 completed for approx. more than 430 enrolled study subjects  | Mandatory                   | +24  |
| M-11 | Interim analysis completed; formal go / no-go decision  | Mandatory                   | +30  |
| M-12 | V3 completed for approx. more than 350 enrolled study subjects  | Mandatory                   | +36  |
| M-13 | V4 completed for approx. more than 350 enrolled study subjects with an sufficient percentage number of disability events at a level of approx. 10% to 15% | Optional                    | +48  |

#### Period of enrollment

Recruitment of 600 eligible study subjects should last no longer than 9 months.

600 MS patients from 20 centers in Germany will be included. During the period of concept development (February and March 2021), we queried the interest of neurological centers in Germany. An overwhelming 83% (25 of 30) of the centers contacted returned a letter of intent indicating their willingness to participate in the study, suggesting recruitment of more than 1,200 study participants. Letters of intent from participating neurological centers, including patient numbers/recruitment estimates, are available upon request.

#### Statement that enrolment is independent of therapeutic decision

Patients meeting the inclusion and exclusion criteria are offered to take part into the study by the participating center. Prior to offering participation the therapeutic decision has already been made.

# Process of enrolment of a patient (therapeutic decision occurring first, invitation to participate, informed consent, etc)

The invitation to participate is issued as soon as the therapeutic decision has been made. The selected patient is informed by the physician. When the conditions and safety concerns have been sufficiently clarified and there are no longer any objections to participation, verbal or written informed consent is obtained. Verbal or written consent is documented.

#### Process of data collection at baseline

If verbal or written informed consent is given the evaluator of the participating center completes the first paper-based case report form (CRF) for the baseline visit (V1) and sends the report via fax or email to the investigator.

## Length of follow-up.

The prospective observational study runs for 24 months plus the additional 9 months enrollment period. In total a baseline visit (V1) and two follow-up visits (V2 and V3) per study subject are planned. The main purpose of these visits is to prescribe and schedule a brain MRI examination with the affiliated radiology center. It is important that brain MRIs are performed annually with a minimum of 11 months apart. If the decision is made to extend the study for another 12 months the individual study subject will be followed for 36 months adding another visit (V4) to the study schedule.

# Statement that no visit or procedures are made mandatory, description of usual care of patient and definition of time points for study data collection

In Germany many MS patients regularly see their physicians on a three-month basis. The EDSS score is frequently taken in normal clinical routine. Annual brain MRI examinations are recommended by national and international guidelines for MS therapy monitoring. The procedures required for this study are part of the standard workup of MS patients in Germany. No visit or procedure is made mandatory. With the schedule of data collection we adhere to the best practices for MS patient management in Germany. No extra procedures are required.

### Overview of Sampling Frame (sites, patients)

In total 600 eligible study subjects shall be sampled at approximately 20 clinical sites across Germany.

#### Part C (closing down of observational prospective study and primary data analysis)

The following table provides checkmarks and / or milestones for Part C:

| ID   | checkmark / milestone description                | Type (mandatory / optional) | Due date (in months after official launch) |
|------|--|-----------------------------|--|
| M-14 | Missing data are collected and databases curated | mandatory                   | +37 (+49 in case of an extension)          |
| M-15 | Analysis of primary data completed and           | mandatory                   | +39 (+51 in case of an                     |

|      | conclusions drawn; final observational study report ready           |          | extension)                        |
|------|---|----------|-----------------------------------|
| M-16 | Manuscript prepared for submission to a clinical /technical journal | optional | +42 (+54 in case of an extension) |

#### **Study Population**

The source population comprises patients with a relapsing-remitting form of MS who are regularly seeing a neurologist (on a three-months basis). In Germany, an estimated 220,000 to 250,000 people currently have MS. MS incidence, i.e. the number of people newly diagnosed with MS in a year, is about a quarter higher in the West than in the East of Germany, with 19 versus 15 new cases per 100,000 inhabitants.

The study shall be conducted in Germany by neurologists who mainly operate in an outpatient setting.

The study population is defined by patients with a diagnosis of relapsing-remitting MS aged 18 – 55 years, who either already receive or are about to receive first-line oral immune therapies with more than 10 T2 lesions or with active disease as defined by clinical (relapses) or imaging features (new/enlarging T2 lesions, Gd-enhancing lesions) according to the Lublin criteria (Lublin et al. 2014).

The reasoning behind targeting this study population is that

- 1. MS patients receiving first-line oral therapies are most likely early-stage patients. Despite undisputed compensatory mechanisms, pathology studies have shown that features of neurodegeneration like axonal transection are quantitatively prominent at early stages of the disease (Kuhlmann et al. 2002).
- 2. MS patients with more than 10 T2 lesions or with active disease are more likely to show disability progression (Tintore et al. 2015)

## **Inclusion Criteria**

- MS, as diagnosed by the revised 2017 McDonald criteria
- Exhibiting a relapsing clinical course and history of brain MRI lesions consistent with MS
- Ages 18 to 55 years, inclusive
- Meet one of the following disease activity criteria
  - a. more than 10 T2 lesions at the time of the first visit OR
  - b. at least one documented relapse with the last 12 months prior to the first visit OR
  - c. documented evidence of at least 1 Gd-enhancing lesion on brain MRI within the last 12 months prior to the first visit OR
  - d. documented evidence of at least one new or one enlarging T2 lesion within the last 12 months prior to the first visit.

- Either receive or about to receive first-line oral immune therapies, such as teriflunomide, ozanimod, dimethylfumarate, ponesimod, and diroximethylfumarate.
- No intention to evaluate the patient to switch from first-line oral immune therapies to other therapy regimens.

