#### **Definitions of Study Variables**

| Event                                  | Study variable   | Operational definition   |
|--|------------------|--|
| Documentation
of medical
history | Age              | Age at index date  |
|  | Gender           | trivial  |
|  | Therapy          | Documentation of previous and current treatments and medications related to MS |
|  | Disease duration | Documentation of time since first MS diagnosis                                 |
| Assessment of                          | Relapse activity | Number of relapses within the last 12 months prior to enrollment               |

| inclusion and exclusion       | T2 lesion load                | Number of T2 lesions at time of assessment as defined by MRI   |
|-------------------------------|-------------------------------|--|
| parameters                    | New / enlarging T2
lesions | Number of new or one enlarging T2 lesions within the last 12 months prior to enrollment as defined by MRI  |
|                               | Gd-enhancing lesion           | Number of Gd-enhancing lesions within the last 12 months prior to enrollment as defined by MRI   |
| Assessment of clinical status | Therapy change                | Therapeutic regimen at the time of visit; therapy is subject to change   |
|                               | Relapse activity              | Number and time of relapses since last visit; assessment and documentation whether EDSS worsening is caused by relapses  |
|                               | Diagnosis                     | Documentation of current diagnosis   |
| Assessment of clinical scores | Disability                    | EDSS is used to quantify disability and disability progression over time in MS. Based on a neurological examination, 8 functional systems (visual, brain stem, pyramidal, cerebellar, sensory, bowel & bladder, cerebral, and other functions) are scored from 0 (no disability) to 5 or 6 (more severe disability). Ambulation is assessed based on the distance the patient is able to walk, whether assistance is required or restrictions are present. |
|                               | Disability progression        | Disability progression is defined as 1.0-point increase for patients with a baseline EDSS of 0 to 5.0, and 0.5 points for scores equal or higher than 5.5.   |

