#### Bias/confounding and effect modification

A potential difficulty is the influence of different treatment regimens during the study. The treatment can impact TVL, new lesions as well as disability worsening. If the groups 1-3 are unbalanced with respect to different treatments results can be biased. A mitigation can be to use the treatment as a covariate in the statistical analysis.

Patients with recent disease activity are included into the study. There should be no intention to switch from first-line oral immune therapies to other therapy regimens when enrolling the patient into the study. Nevertheless, some patients might switch from first-line oral immune therapies to a second line therapy. For these patients the phenomenon of pseudo-atrophy might occur as it was described in several studies (generally assumed to be due to the resolution of inflammatory edema). Measures TVL needs to be interpreted with caution for these patients. MRI data needed to be excluded if the therapy switch happened less than 6 months before the MRI.

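### Patients starting oral therapy are pooled with established users, and the pseudo-atrophy rule covers only later switches, so any start-of-therapy volume change enters thalamic volume loss unadjusted

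*Protocol*

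**What the plan says.** Section 3, Inclusion Criteria, admits patients who "Either receive or about to receive first-line oral immune therapies". The Study Population text pools the same two groups. No minimum time on therapy, stratum or subgroup by starter status is given. Recent inflammation is not required: one activity criterion is "more than 10 T2 lesions at the time of the first visit OR", with relapse or active lesions as alternatives.

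On timing, the protocol states "Prior to offering participation the therapeutic decision has already been made" and "The invitation to participate is issued as soon as the therapeutic decision has been made". It does not say whether first dose comes before or after the V1 MRI. Under Length of follow-up, "brain MRIs are performed annually with a minimum of 11 months apart".

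Section 5, Bias/confounding and effect modification, notes that "some patients might switch from first-line oral immune therapies to a second line therapy". It says pseudo-atrophy might occur in these patients, attributes it to resolving inflammatory edema, and concludes: "MRI data needed to be excluded if the therapy switch happened less than 6 months before the MRI". It offers treatment as a possible covariate.

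The primary endpoint is a plain Pearson coefficient between annual EDSS change and annual thalamic volume change, with TVL taken from the baseline to the last scan. S1 and S2 use TVL split at cut-offs. The baseline variables include "Documentation of previous and current treatments and medications related to MS".

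**The concern.** The protocol accepts that a therapy change can alter thalamic volume for reasons other than neurodegeneration, and sets a rule against it. The rule is written for one kind of change, a later move to second-line therapy. The cohort contains another kind by design: a first start of oral therapy around enrolment. For those patients the measurement interval can span the start, and nothing in the stated primary analysis separates them from established users.

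At stake is what the correlation means. If starters differ from established users in mean volume change, that difference adds noise to TVL. If they also differ in mean EDSS slope, the pooled coefficient mixes a between-group contrast with the within-patient association the study wants to show. In S1 and S2 the same shift could reclassify a starter from normal to pathological TVL.

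**Working it through.** **1. Does the 6-month rule catch a start near V1?** Suppose therapy starts t months after the V1 MRI. V2 is at least 11 months after V1, so an interval of exactly 11 months leaves 11 - t months between start and V2. That is under 6 only if t exceeds 5. For a start within 5 months after V1 the rule never acts, even if a first start is read as a switch. If V2 were dropped, the V1-to-V3 interval would still span the start. If the first dose came less than 6 months before V1, a broad reading would drop the V1 scan, but the text speaks of moves to second-line therapy and does not give that reading.

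**2. The plan's own figures.** Inputs (Power/Sample Size): r = 0.15, type I error 0.05, type II error 0.20. Fisher z, two-sided: n = ((1.960 + 0.842)/atanh(0.15))² + 3, with atanh(0.15) = 0.1511, gives 346.6, so 347. This matches. Expected at month 24: 600 × 0.85² = 433, as in the attrition table. Power at r = 0.15 is 80% at 347 and 88% at 433. The concern does not touch this arithmetic.

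**3. Effect of a starter shift on r (assumptions).** Let f be the share of starters, dT their mean extra volume loss, and dE the amount by which their mean EDSS slope is lower, both in within-group SDs. Within each group r = -0.15, negative because the hypothesis is inverse. Then

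r(pooled) = (-0.15 + f(1-f)·dT·dE) / sqrt[(1 + f(1-f)·dT²)(1 + f(1-f)·dE²)]

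Example: f = 0.5, dT = 0.5, dE = 0.3 gives (-0.15 + 0.0375)/sqrt(1.0625 × 1.0225) = -0.1125/1.0423 = -0.108.

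Power = Φ(sqrt(n-3)·atanh|r| - 1.960).

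| f | dT | dE | pooled r | n=347 | n=433 |
|---|---|---|---|---|---|
| 0.2 | 0.3 | +0.2 | -0.139 | 74% | 83% |
| 0.3 | 0.5 | +0.3 | -0.114 | 57% | 66% |
| 0.5 | 0.5 | +0.3 | -0.108 | 52% | 61% |
| 0.5 | 0.5 | 0 | -0.146 | 78% | 86% |
| 0.2 | 0.3 | -0.2 | -0.158 | 84% | 91% |
| 0.5 | 0.5 | -0.3 | -0.180 | 92% | 97% |

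In the last two rows the higher figure is not a gain: the correlation is overstated relative to -0.15.

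**4. S1.** With 5% against 15% progression in 196 and 98 patients, the usual two-proportion normal test (pooled variance under the null) gives 80% power, as planned. Assume 10% or 20% of group 2 are starters misclassified by a volume shift who carry the group 1 risk. The group 2 rate becomes 0.9 × 15% + 0.1 × 5% = 14%, or 0.8 × 15% + 0.2 × 5% = 13%, and power falls to 74% or 66%. If misclassified starters progressed more often than group 2, the contrast would be inflated instead.

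**The case against.** The strongest reply is that the premise is not in the documents. The protocol says only that pseudo-atrophy might occur, and says it of second-line switches. It nowhere states that starting a first-line oral drug shrinks the thalamus. A reader might infer that every starter's TVL is contaminated, or that V1 always precedes first dose. Neither is supported: the enrolment text orders decision and invitation, not first dose and scan, and the schedule footnote does not tie the MRI closely to clinical scoring.

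A reader might also infer that the correlation must be diluted, because starters would have recent activity and then recover on EDSS. Both groups face the same entry criteria, and more than 10 T2 lesions suffices without recent inflammation. The fall to 52% depends almost wholly on the assumed EDSS difference.

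The covariate table also lists baseline lesion activity and baseline EDSS as factors to control, which are partial proxies for the mechanism, and treatment history is recorded. Finally, covariate coding usually belongs in the SAP.

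These points limit the size and certainty of the concern. They do not remove it. The listed controls have no place in the endpoint as stated, and treatment is worded as an optional covariate described by drug, not by time since start. The pooled population and the pseudo-atrophy rule are fixed in the protocol itself, so a gap between them is a protocol matter.

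**Conclusion.** The concern holds in conditional form. Any early treatment-related volume change in starters scanned before or soon after first dose enters baseline-to-last-scan TVL without adjustment, and the protocol's pseudo-atrophy rule does not reach it. Whether such a change occurs with first-line oral therapy, how large it is, and how many starters there will be cannot be established from the protocol.

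The effect can go either way. With starters at 20% to 50% and a volume shift of 0.3 to 0.5 SD, the result depends mainly on whether starters' EDSS slope also differs. A volume shift alone costs little. An EDSS difference of 0.2 to 0.3 SD can weaken the correlation materially or inflate it. At the 433 patients expected, power is 61% to 83% with a lower EDSS slope in starters, 86% with no difference, and 91% to 97% with a higher one. This is a worthwhile, inexpensive improvement and not a flaw that invalidates the design.

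**What to change.** - Make sure the start date of the current oral therapy is captured with the treatment history at V1. The CRF is not shown, so it may already be there.
- For analysis, define a starter as a patient whose therapy began after the V1 MRI or less than 6 months before it, borrowing the interval in the protocol's own pseudo-atrophy rule.
- Adjust the primary correlation for starter status (partial correlation), and stratify S1 and S2 by it.
- Report the primary result in non-starters as a sensitivity analysis.
- Say in section 5 how a start of therapy at enrolment is treated, so that it agrees with the inclusion criteria.

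The cost is about one degree of freedom (348 instead of 347 patients), with no added visit or scan. Adjustment removes a mean difference between the groups but not variation in response among starters; the non-starter analysis addresses that. Its sample is smaller. If starters are 20% of 433, about 346 remain and power at r = 0.15 is 80%. If they are 50%, about 216 remain and power is 60%. For that reason non-starters should be a sensitivity analysis, not the primary one.
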